6.1.1.1. ORR

The ORR will be calculated as the number of patients with a confirmed BOR of CR or PR divided by the number of patients in the Efficacy Evaluable population. Patients without at least 1 post-baseline RECIST assessment will be treated as non-responders (i.e., these patients will contribute to the denominator, but not the numerator).

6.1.1.2. DOR

DOR is defined as the time from the date of the first response (CR or PR), whichever occurs first, to the date of PD or death from any cause, whichever occurs first. DOR is only defined for patients who have a confirmed BOR of CR or PR.

Per the BOR definition, patients with an overall response of CR or PR must have a repeat tumor assessment performed no less than 4 weeks after the criteria for response are first met. The first date at which a CR or PR response was noted will be used to calculate DOR, not the date of the confirmatory tumor assessment.

Patients who started a new anti-cancer therapy prior to documented PD or death will be censored at the last radiological assessment prior to initiation of new anti-cancer therapy. Patients who did not have PD or death or new anti-cancer therapy will be censored at the date of their last radiological assessment. Patients who had PD or death after missing 2 or more consecutive radiological assessments (PD or death date - last radiological assessment date +1 \geq 105 days or \geq 231 days if the assessment schedule has changed from every 6 weeks [+1 week] to every 12 weeks [+3 weeks] after Week 36 or after discontinuing from study treatment per local requirements). will be censored at the date of their last radiological assessment before the missing radiological assessment.

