3.2. Study Overview

This Phase 2 study is designed to evaluate the efficacy and safety of MIRV in patients with recurrent platinum-sensitive, high-grade serous epithelial ovarian cancer, primary peritoneal, or fallopian tube cancer (EOC), whose tumors express a high level of FR α , referred to throughout as rPSOC (recurrent platinum-sensitive ovarian cancer). Patients will have had at least 2 prior lines of therapy. These will include at least 2 lines of platinum-containing therapy or 1 line with a documented platinum allergy. All patients will be, in the opinion of the Investigator, appropriate for non-platinum single-agent therapy for their next line of therapy. FR α positivity will be defined by the Ventana FOLR1 (FOLR1-2.1) CDx assay (Ventana FOLR1 Assay)..

Eligible patients will receive MIRV 6mg/kg AIBW Q3W until disease progression, unacceptable toxicity, withdrawal of consent, death, or until the Sponsor terminates the study (whichever comes first).

Tumor assessments, including radiological assessments by CT/MRI scans will be performed at Screening and subsequently every 6 (± 1) weeks from C1D1 for the first 36 weeks then every 12 (± 3) weeks until disease progression, death, the initiation of subsequent anticancer therapy, or patient's withdrawal of consent, whichever occurs first. CT/MRI scans will be collected for sensitivity analysis by blinded independent central review (BICR)

Patients who discontinue MIRV for reasons other than PD will continue with tumor assessments until documentation of PD or the start of a new anticancer therapy, whichever comes first. Prior to Week 36 (from C1D1), assessments should occur every 6 weeks (± 1 week) as allowed by local requirements but must occur at an interval of no more than 12 weeks. After Week 36, assessments will occur every 12 weeks (± 3 weeks) until documentation of PD per RECIST v1.1 ([Eisenhauer 2009](#)) or the start of new anticancer therapy.

All patients who discontinue MIRV will be followed for survival every 3 months (± 1 month) until death, lost to follow-up, withdrawal of consent for survival follow-up, or End of Study (EOS) (whichever comes first). Additional survival follow-up calls may occur periodically, if needed.

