6.1.2. PFS

PFS is defined as the time from the date of first dose of MIRV until the date of PD or death from any cause, whichever occurs first. PFS is defined based on radiological assessments and determined by the Investigator. Clinical progression is not considered a progression endpoint.

[Table 3](#) summarizes the rules to be used for PFS. When an analysis cutoff date is implemented, only data (deaths and radiological assessments) occurring on or prior to the cutoff date will be used for analysis.

Table 3: PFS Definitions

Situation	Date of PFS Event or Censoring	Outcome
No post-baseline radiological assessments, and patient did not die within 105 days of first dose	Date of first dose	Censored
No post-baseline radiological assessments, and patient died within 105 days of first dose	Date of death	Death
Death	Date of death	Death
Radiological Progression	Date of first radiological assessment indicating progression .	Progression
New anti-cancer therapy prior to PD or death (including palliative radiotherapy during study treatment)	Date of last radiological assessment prior to the start of the new anticancer therapy	Censored
No death or PD	Date of last radiological assessment	Censored
PD or death after missing 2 or more consecutive radiological assessments (PD or death date - last radiological assessment date +1 \geq 105 days or \geq 231 days if the assessment schedule has changed from every 6 weeks [+1 week] to every 12 weeks [+3 weeks] after Week 36 or after discontinuing from study treatment per local requirements).	Date of last adequate radiological assessment showing no PD	Censored

6.1.3. OS

OS is defined as the time from the date of first dose until the date of death from any cause.

Patients who are alive or lost to follow-up at the analysis are censored at the last known date at which they were known to be alive.

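### The 105/231-day missed-scan rule for DOR and PFS does not correspond to two missed scans when the gap spans the Week 36 schedule change

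*SAP*

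**What the plan says.** SAP 3.2 sets scans "every 6 (± 1) weeks from C1D1 for the first 36 weeks then every 12 (± 3) weeks". SAP 6.1.1.2 states the censoring rule for DOR first in words: "Patients who had PD or death after missing 2 or more consecutive radiological assessments". It then gives a day count. The gap is "PD or death date - last radiological assessment date +1", and the limit is 105 days, or 231 days "if the assessment schedule has changed from every 6 weeks" to every 12 weeks after Week 36. The longer limit has a second trigger, a schedule that changed "or after discontinuing from study treatment per local requirements". A patient caught by the rule "will be censored at the date of their last radiological assessment before the missing radiological assessment".

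Table 3 in SAP 6.1.2 applies the same words and the same two limits to PFS ("PD or death after missing 2 or more consecutive radiological assessments"). SAP 6.5 carries the methods over to the BICR analyses of DOR and PFS. SAP 4.11.2 says that the secondary endpoints have no formal test.

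**The concern.** The words describe a count of missed visits, and the day limits are meant to implement that count. There is one limit for the 6-week phase and one for the 12-week phase, but none for a gap that starts in the first phase and ends in the second. The text also leaves open at what moment the schedule counts as changed: at the last scan, or at the PD or death.

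Two programmers could therefore derive different event indicators from the same data, and either could depart from the stated rule. What is at stake is whether some late-detected progressions and some deaths enter the Kaplan-Meier estimates of DOR (the key secondary endpoint) and PFS as events or as censored observations.

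**Working it through.** **Inputs.** Scans fall due at Weeks 6, 12, 18, 24, 30 and 36 (±1 week), then at Weeks 48, 60, 72 and so on (±3 weeks), from SAP 3.2. The gap is the event date minus the last scan date, plus 1. The limits are 105 and 231 days, from SAP 6.1.1.2 and Table 3.

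**Step 1: reproduce the SAP's limits.** The SAP does not say how they were built. The formula 7 × (2 × interval + 3 × window) fits both exactly:
- 6-week phase: 7 × (2 × 6 + 3 × 1) = 7 × 15 = 105
- 12-week phase: 7 × (2 × 12 + 3 × 3) = 7 × 33 = 231

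On this inferred construction, 231 days assumes that both intervals are 12-weekly.

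**Step 2: inside the 6-week phase.** The nominal gap is 7 × (weeks apart) + 1. The window range is 7 × (weeks apart ± both windows) + 1.
- One missed scan, 12 weeks apart: 85 days (71 to 99)
- Two missed scans, 18 weeks apart: 127 days (113 to 141)

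For PD found at a scheduled scan, 105 separates the two cases.

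**Step 3: gaps that cross Week 36.** For a scan on each side of the change, both windows add to 1 + 3 = 4 weeks. For Week 24 to Week 48 this gives 7 × 20 + 1 = 141 to 7 × 28 + 1 = 197.

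| Last scan to PD (weeks) | Missed | Nominal gap | Window range | Schedule judged at event (231) | Schedule judged at last scan (105) |
|---|---|---|---|---|---|
| 24 to 48 | 2 | 7 × 24 + 1 = 169 | 141–197 | event at every date (wrong) | censored |
| 18 to 48 | 3 | 7 × 30 + 1 = 211 | 183–239 | event at nominal dates (wrong); censored from 231 | censored |
| 30 to 60 | 2 | 7 × 30 + 1 = 211 | 183–239 | event at nominal dates (wrong); censored from 231 | censored |
| 30 to 48 | 1 | 7 × 18 + 1 = 127 | 99–155 | event | censored at nominal dates (wrong); event below 105 |

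Two further cases, Weeks 12 to 48 (four missed) and 24 to 60 (three missed), are censored at the nominal 253 days on either reading. Their range is 225 to 281, so judged at the event they can fall short of 231 at the window edge.

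**Step 4: deaths.** Take a last scan at Week 24 with Weeks 30 and 36 missed. Judged at the event, a death after the Week 36 window closes is an event up to a gap of 230 days, that is to Week 24 + 229/7 = 56.7.

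**Step 5: would fixed limits by last scan do instead?** Try 105 days for a last scan up to Week 24, a separate limit for Week 30, and 231 days from Week 36.
- For Week 30, one missed scan gives at most 155 days and two give at least 183, so any limit from 156 to 183 works.
- At nominal dates the set then classifies every case correctly.
- At window edges it does not. Two missed scans can give 225 days (Weeks 36 to 72) or 211 days (Weeks 48 to 84), both below 231. One missed scan in the 12-week phase can also reach 211 days (Weeks 48 to 72), so no cut separates one from two perfectly.
- If the off-treatment trigger were dropped, a patient on 12-week scans with a last scan at Week 12, Week 24 missed and PD at Week 36 has a gap of 7 × 24 + 1 = 169 days. That is one missed scan, and 105 would censor it. With the ±3-week window in footnote n of protocol Table 2, an on-time scan 15 weeks later gives 7 × 15 + 1 = 106 days and would also be censored.

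**The case against.** The strongest reply is that the SAP can be read with the schedule judged at the last scan. The gaps from Weeks 24 to 48, 18 to 48 and 30 to 60 then all exceed 105 days and are censored as intended. This stands. A reader might infer that the rule counts as events what it says to censor, but the documents support that only if the event date governs, and they do not settle the matter. The reply does not rescue the rule, because the last-scan reading wrongly censors a patient who missed only the Week 36 scan.

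It can also be said that the effect is small. DOR and PFS are summarised without a test, and patients who start new anticancer therapy before PD or death are censored under a separate provision, which narrows the group further. Both points stand and limit the weight of the concern.

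Two stronger inferences are not supported. One is that the medians are distorted because the affected weeks lie where the median will fall. Neither document assumes a median PFS or DOR for this study, and DOR runs from first response, so weeks from Cycle 1 Day 1 do not map onto DOR time. The other is that progression is misdated by about seven months. The 30 weeks behind that figure run from the last clean scan, whereas scheduled detection could not come before the first missed visit. At nominal dates the delay in the three cases is at most 48 − 30 = 18 weeks, 48 − 24 = 24 weeks and 60 − 36 = 24 weeks, or about 4.1 to 5.5 months at 30.4375 days per month. Dates of death are not detected late at all.

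**Conclusion.** The concern holds as a defect at the schedule change. On either reading, the 105/231-day rule departs from the SAP's own criterion of two or more missed scans for some gaps that cross Week 36. The error runs in opposite directions on the two readings. Only the Week 24 to Week 48 case fails at every date within the windows; the other cases in the table fail at nominal dates and can come right at the window edge.

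The affected results are DOR and PFS, by Investigator and by BICR, all descriptive. The test of ORR does not use this rule. The documents do not allow the number of affected patients, or the shift in any estimate, to be derived. The result rests on the schedule and windows in SAP 3.2 and on PD being dated at a scheduled scan. This is a worthwhile clarification, not a threat to the trial's main conclusion.

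**What to change.** In SAP 6.1.1.2 and Table 3, replace the day limits with a count. Suggested sense: *censor at the last adequate scan when two or more consecutive scheduled assessment windows closed without a scan between that scan and the PD or death, using the schedule that applied to the patient at each visit.* That schedule is 6-weekly to Week 36, 12-weekly after, or the off-treatment schedule allowed by local requirements.

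Three details need stating:
- How a scan taken outside any window is assigned to a visit.
- Which off-treatment schedule the count uses. Footnote n of protocol Table 2 gives both 12-weekly scans and 6-weekly scans with a 12-week maximum before Week 36, and these statements must be reconciled.
- Whether the count is meant to apply to deaths in the 6-week phase. With a last scan on its nominal date, the second missed window closes at a gap of 7 × 13 + 1 = 92 days, so deaths at 92 to 104 days, now events, would be censored.

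Fixed limits by last scan are a weaker substitute, sound only at nominal dates and only if the off-treatment 12-week branch is kept.

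The cost is a short SAP revision and a small programming change, with no new data. SAP 2.1 allows changes before final database lock. After lock, the count could be run as a sensitivity analysis documented in the study report.

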6.1.1.3. Time to Response

Time to response (TTR) is defined as the time from the date of first dose of MIRV until the date of the first observed CR or PR. TTR is only defined for patients who have a confirmed BOR of CR or PR.

6.1.2. PFS

PFS is defined as the time from the date of first dose of MIRV until the date of PD or death from any cause, whichever occurs first. PFS is defined based on radiological assessments and determined by the Investigator. Clinical progression is not considered a progression endpoint.

[Table 3](#) summarizes the rules to be used for PFS. When an analysis cutoff date is implemented, only data (deaths and radiological assessments) occurring on or prior to the cutoff date will be used for analysis.

Table 3: PFS Definitions

Situation	Date of PFS Event or Censoring	Outcome
No post-baseline radiological assessments, and patient did not die within 105 days of first dose	Date of first dose	Censored
No post-baseline radiological assessments, and patient died within 105 days of first dose	Date of death	Death
Death	Date of death	Death
Radiological Progression	Date of first radiological assessment indicating progression .	Progression
New anti-cancer therapy prior to PD or death (including palliative radiotherapy during study treatment)	Date of last radiological assessment prior to the start of the new anticancer therapy	Censored
No death or PD	Date of last radiological assessment	Censored
PD or death after missing 2 or more consecutive radiological assessments (PD or death date - last radiological assessment date +1 \geq 105 days or \geq 231 days if the assessment schedule has changed from every 6 weeks [+1 week] to every 12 weeks [+3 weeks] after Week 36 or after discontinuing from study treatment per local requirements).	Date of last adequate radiological assessment showing no PD	Censored

6.1.3. OS

OS is defined as the time from the date of first dose until the date of death from any cause.

Patients who are alive or lost to follow-up at the analysis are censored at the last known date at which they were known to be alive.

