7.13. Tumor Response Assessment

7.13.1. Radiological Imaging

Radiologic tumor evaluation by CT or MRI of chest, abdomen, and pelvis will be performed within 28 days before first dose of study drug and every 6 weeks (\pm 1 week) from C1D1 for the first 36 weeks on study and every 12 weeks (\pm 3 weeks) thereafter (Table 2). Patients who discontinue study treatment for reasons other than PD will continue with tumor assessments until documentation of PD or the start of a new anticancer therapy, whichever comes first. Prior to Week 36 (from C1D1), assessments should occur every 6 weeks (\pm 1 week) as allowed by local requirements but must occur at an interval of no more than 12 weeks. After Week 36, assessment will occur every 12 weeks (\pm 3 weeks) until documentation of PD or the start of new anticancer therapy. The same method of radiographic assessment used at Screening must be used at all subsequent radiographic evaluations. Copies of all imaging scans must be obtained and sent to a central imaging vendor designated by ImmunoGen as outlined in the Imaging Manual. The central imaging vendor will assess the quality of the images. The imaging vendor will be responsible for the formation and management of the BICR which will be used as a sensitivity analysis of ORR, DOR, and PFS by the Investigator.

Tumor response will be assessed by the Investigator using RECIST v1.1 (Eisenhauer 2009). Response as determined by the Investigator will be recorded in the clinical trial database.

The central imaging vendor will ensure that the central radiologists remain blinded to the local assessment from the Investigator and other unblinding information. This and all other imaging procedures will be documented in an independent review charter agreed upon between ImmunoGen and the imaging vendor before initiation of any BICR reviews.

Note: It is very important that the same method of radiologic assessment be used throughout the study and that the same lesions are followed.

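### SAP Table 3's 105-day missed-scan rule does not restrict its anchor to post-baseline scans, so read literally it can censor a Week 11–13 progression after one missed scan, before PFS time zero

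*SAP*

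**What the plan says.** SAP Section 6.1.2 starts the PFS clock at first dose: "PFS is defined as the time from the date of first dose of MIRV until the date of PD or death from any cause". Table 3 then gives seven situations. Three matter here.

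- **Row 1**, "No post-baseline radiological assessments, and patient did not die within 105 days of first dose": censored at first dose.
- **Row 2**, "No post-baseline radiological assessments, and patient died within 105 days of first dose": an event on the date of death.
- **Last row**, "PD or death after missing 2 or more consecutive radiological assessments (PD or death date - last radiological assessment date +1" is at least 105 days, or "231 days if the assessment schedule has changed from every 6 weeks" to every 12 weeks: censored at "Date of last adequate radiological assessment showing no PD".

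Rows 1 and 2 specify post-baseline assessments and count from first dose. The last row does neither. The SAP overview (Section 3.2) treats the screening scan as one of the radiological assessments: "radiological assessments by CT/MRI scans will be performed at Screening and subsequently every 6" weeks. Protocol Section 7.13.1 says that this first evaluation "will be performed within 28 days before first dose of study drug". The table does not say which row applies when a patient fits more than one.

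**The concern.** The last row has a verbal condition (two or more consecutive scans missed) and a date formula that is meant to implement it. The two agree when an earlier post-baseline scan exists. They can disagree when the progression scan is itself the first post-baseline scan. The only earlier assessment is then the screening scan, and up to 28 days before dosing are added to the gap. Rows 1 and 2 do not cover this patient, because her progression scan is a post-baseline assessment.

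A programmer who codes the formula as written would censor a true progression after one missed scan. The censoring date would be the screening scan, which precedes the PFS origin. Whether the resulting negative time is dropped or set to zero, the patient is never in the risk set at any later time. The error runs one way, towards longer PFS, in a single-arm study with no control group to share it. SAP Section 6.5 applies the same methods to PFS by BICR.

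**Working it through.** **Inputs.** Scans every 6 weeks (±1) to Week 36, then every 12 weeks (±3), counted from first dose (SAP 3.2). Screening scan up to 28 days before first dose (Protocol 7.13.1). Planned efficacy evaluable patients: 69 (SAP 3.2.2); PFS uses that population (SAP 6.3.2).

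**1. The plan's own thresholds.** Threshold = 7 × [2 × (interval + window) + window].
- 6-weekly: 7 × [2 × (6+1) + 1] = 7 × 15 = 105 days.
- 12-weekly: 7 × [2 × (12+3) + 3] = 7 × 33 = 231 days.

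Both are reproduced, so the formula was built for gaps on the on-study schedule.

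**2. Earlier post-baseline scan exists.** On the 6-weekly schedule, one missed scan gives at most (12+2) × 7 + 1 = 99 days, below 105. Words and formula agree.

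**3. Progression scan is the first post-baseline scan.** Let t be days from first dose to the event and b be days from screening scan to first dose. Read literally, the rule fires when t + b + 1 ≥ 105, that is, when b ≥ 104 − t.

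| Progression at | t | b needed | Gap at b = 28 | Gap from first dose | Share caught, b uniform on 1–28 (assumed) |
|---|---|---|---|---|---|
| Week 7 (no scan missed) | 49 | 55 (not possible) | 78 | 50 | 0 |
| Week 11 (one missed) | 77 | ≥ 27 | 106 | 78 | 2/28 = 7% |
| Week 12 (one missed) | 84 | ≥ 20 | 113 | 85 | 9/28 = 32% |
| Week 13 (one missed) | 91 | ≥ 13 | 120 | 92 | 16/28 = 57% |

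Counting from first dose, none of these reaches 105. Week 18 progression after two missed scans gives 126 + 1 = 127 and is still censored, as the words intend.

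**4. Deaths with no post-baseline scan.** With b = 28, the literal formula fires from t = 104 − 28 = 76. Row 2 makes deaths within 105 days of first dose events, so from day 76 to day 105 a patient could fit both rows. Even with the gap counted from first dose, t = 104 gives 105 and t = 105 gives 106, so an overlap at days 104–105 remains.

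**5. Size, by arithmetic.** If k patients who fail before the time point leave the risk set at time zero, and there is no other censoring, a true proportion S becomes S × 69/(69 − k). For S = 50%:
- k = 1: 50 × 69/68 = 50.7%
- k = 2: 50 × 69/67 = 51.5%
- k = 3: 50 × 69/66 = 52.3%

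The documents give no basis for k.

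**6. Size, by simulation.** This used 69 patients, 400 replicates per setting, exponential PFS with median 4, 7 or 10 months, and 2%, 5% or 10% of scans missed. All of these are assumptions. The literal reading was compared with counting from first dose.

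| Screening lead (assumed) | Mean patients affected | 3-month PFS | Median PFS |
|---|---|---|---|
| Uniform, 1–28 days | 0.1–0.8 | +0.1 to +0.7 points | +0.00 to +0.07 months |
| All 28 days (worst case) | 0.2–2.3 | +0.25 to +2.2 points | about +0.01 to +0.27 months |

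**The case against.** The best defence is that the SAP nowhere says the rule runs from the screening scan. The row's stated condition is two or more missed scans, which a patient with one missed scan does not meet, and the formula can be read as only implementing those words. Rows 1 and 2 apply the same 105 days from first dose, which suggests first dose was the intended anchor. A screening scan is also an odd candidate for one showing no progression: progression is judged after baseline (Protocol Appendix B), and inclusion criterion 5 requires radiographic progression on or after the last therapy.

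Much of this stands. The screening anchor is a literal reading of an unrestricted term, not a stated rule. But the formula is the only operational definition given, it conflicts with the words for these patients, and the table does not say which governs. If the screening scan does not qualify as the censoring scan, the row offers no censoring date at all, since it lacks row 1's fallback to first dose.

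A reader might also infer that the table censors early deaths. It does not say so. Row 2 is written for exactly those patients and makes them events. What remains is the unstated order. It needs stating, because the last row must override the general death and progression rows to have any effect, so a first-match rule cannot be assumed.

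Nor do the documents support the inference that the earliest failures are lost. Progression at the Week 6 scan, progression at Week 12 after an attended Week 6 scan, and deaths before day 76 are untouched. Patients moved to the 12-weekly schedule after stopping treatment fall under the 231-day limit.

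**Conclusion.** The concern holds as a conditional defect in wording. On the literal formula, a patient still on the 6-weekly schedule who missed only the Week 6 scan and progresses at Week 11, 12 or 13 can be censored before time zero, given a screening lead of at least 27, 20 or 13 days. For deaths, only the missing row order is at issue.

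A reader might infer a material inflation of PFS. The figures do not show one: under uniform screening leads, fewer than one patient of 69 is affected on average, and the larger effects need every screening scan to fall at day 28. All sizes rest on assumed median PFS, missed-scan rates and screening leads, which the documents do not give.

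PFS is a secondary endpoint with no formal test (SAP 4.11.2). ORR is unaffected, because a patient whose first scan shows progression is a non-responder. DOR is unaffected, because it starts at a post-baseline response. The change is still worth making: the written rule can return a wrong result, always in the favourable direction, and correcting it is cheap.

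**What to change.** In SAP Table 3, last row:

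1. Measure the gap from the later of the first-dose date and the last adequate post-baseline scan before the event.
2. State that the censoring date is never earlier than first dose.
3. State that rows 1 and 2 take precedence over the last row when there is no post-baseline scan.

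Apply the same wording to PFS by BICR. Progressions at Weeks 11–13 after one missed scan then count as events, and true two-scan gaps are still censored.

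The cost is a sentence or two in the table and about one line of programming. SAP Section 2.1 allows changes before final database lock; after that, the handling should be documented in the study report as a deviation. The only downside for the sponsor is that PFS may look slightly less favourable.
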